7.2. KEY DEFINITIONS

Study day 1 is the day of the first dose of Optivate[®]. This is expected to be the date of the Baseline Visit. Study day -1 is the day prior to this.

7.3. MISSING DATA

All available data will be used in the statistical analysis. There will be no imputation for missing data.

Sponsor: BPL

Protocol: 8VWF07

Version: 1.0

Statistical Analysis Plan

7.4. VISIT WINDOWS

Visit windows will not be applied. All data will be summarised according to the nominal visit at which they were collected.

Subjects who withdraw from the study are to complete the End of Study/Visit 4 CRF pages. For summaries based on the Safety Population, these data will be summarised under 'End of Study'. An additional summary will also be provided for 'Visit 4', which will only include data from subjects who do not withdraw.

7.5. POOLING OF CENTRES

Data across all centers will be pooled for statistical analysis. Due to the small number of subjects to be recruited, center will not be included as a factor in any of the statistical models.

7.6. SUBGROUPS

With the exception of the possible analyses based on basal FVIII values, described in Section 6.3, no subgroup summaries are planned.

Sponsor: BPL

Protocol: 8VWF07

Version: 1.0

Statistical Analysis Plan

8. DEMOGRAPHIC, OTHER BASELINE CHARACTERISTICS AND MEDICATION

8.1. SUBJECT DISPOSITION AND WITHDRAWALS

The number of subjects screened and enrolled will be presented. The number and percentage of subjects completing treatment and withdrawing from treatment will be summarised along with the reason for withdrawal.

The number and percentage of subjects in the Safety and Per Protocol Populations will be presented.

Inclusion and exclusion criteria will be listed only.

Time on study (days) is defined as:

Time on Study (Days) = Date of Visit 4 (end of study visit)/withdrawal visit - Date of Baseline visit + 1

Time on study in months and years will also be calculated by dividing the time on study calculated in days by 28 and 365 respectively.

Time on study calculated in each of days, months and years will be summarized for the Safety Population.

Total time on study will be presented in both months and years for the Safety Population. These will be calculated by taking the mean time on study in months/years respectively and multiplying by the number of subjects in the Safety Population.

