9 SUBJECT WITHDRAWAL

Subjects may stop study treatment for any of the following reasons:

• Withdrawal of consent.

- Significant protocol deviation.
- Lost to follow-up.
- Incidental illness.
- Occurrence of adverse events (AEs) not compatible with the continuation of the subject's participation in the study, in the Investigator's opinion (*eg* anaphylactic or other severe/serious reaction to infusion, development of inhibitor).
- Investigator's request.
- Requirement for therapeutic intervention prohibited by the protocol *eg* FVIII containing product or antifibrinolytics agents (expect during surgery).
- Premature termination of the trial by BPL on account of an unacceptable risk-benefit ratio. If this occurs, BPL or BPL's representatives will notify the regulatory authorities, ethics committees and Investigators of the reason for premature study termination, within 15 days from the study being halted.
- Subject/guardian is unco-operative and non-compliant with respect to provisions of the protocol.
- Trial stopped by BPL as 10 evaluable subjects have 100 EDs with Optivate[®].
 NB:this may mean that the last two subjects enrolled into the study may receive a shorter treatment period.

The clinical Investigator may also remove a subject if, in his/her opinion, it is in the best interests of the subject.

Subjects are free to withdraw from the study at any time without providing reason(s) for withdrawal and without prejudice to further treatment. The reason(s) for withdrawal will be documented where possible, particularly where withdrawal is a consequence of an adverse event. The subject's primary care physician (where applicable) will be informed of the reason for withdrawal.

Data collected up until a subject's withdrawal from the study, including data for screen failures, will be retained on the clinical database and used in the analysis and clinical study report.

Subjects withdrawing from the study will be requested to complete the same final assessments as subjects completing the study according to the protocol, particularly safety assessments (see Section 7.4). If there is a medical reason for withdrawal, the subject will remain under the supervision of the Investigator until in satisfactory health or the subject's condition has stabilised.

Reasonable efforts will be made to contact subjects who are lost to follow-up. These efforts must be documented in the subject's medical records.

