6.2. SAFETY POPULATION

The Safety Population is defined as all subjects who received at least part of one dose of Optivate[®]. The Safety Population will be used for all analyses of safety endpoints, and as a secondary population for the analysis of efficacy endpoints.

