7. GENERAL ASPECTS FOR STATISTICAL ANALYSIS

7.1. GENERAL METHODS

Statistical outputs will be generated using SAS version 9.3 (or later).

The study only has one treatment and so all summary tables will have a single results column for Optivate[®]. However, if subjects suffering from severe haemophilia A with basal FVIII values of < 2% rather than < 1% are recruited into the study, an additional two results columns will be presented, one for subjects with a basal FVIII < 1%, and one for subjects with a basal FVIII $\ge 1\%$ (see Section 6.3).

Continuous variables will be summarised using the number of observations (n), mean, 95% confidence interval for the mean, standard deviation (SD), median, minimum, and maximum. Minima and maxima will be quoted to the number of decimal places as recorded in the CRF, means and medians will be quoted to one further decimal place, and SDs will be quoted to one further decimal place than the mean value. Categorical variables will be summarised using number of observations (n), frequency and percentages of subjects. Percentages will be rounded to one decimal place, with the exception of 0% and 100%, which will be presented to no decimal places.

All relevant subject data will be included in listings. All subjects entered into the database will be included in subject data listings.

Data from unscheduled visits will not be included in the summary tables. These data will be listed only.

Where multiple data/results are available at a given visit for the same parameter, the first non-missing result will be used in the summary tables. All data will however be listed.

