14.2.4. Column Headers

- Column headings should be displayed immediately below the solid line described above in initial upper-case characters.
- In the case of efficacy tables, the variable (or characteristic) column will be on the
 far left followed by the treatment group columns and total column (if applicable).
 P-values may be presented under the total column or in separate p-value column (if
 applicable). Within-treatment comparisons may have p-values presented in a row
 beneath the summary statistics for that treatment.
- For numeric variables, include "unit" in column or row heading when appropriate.
- Population sizes will be presented for each treatment group in the column heading as (N=xx) (or in the row headings if applicable). This is distinct from the 'n' used for

Sponsor: BPL
Protocol: 8VWF07

Version: 1.0

Statistical Analysis Plan

the descriptive statistics representing the number of subjects in the population with the respective data.

• The order of treatments in the tables and listings will be Placebo first in the case of placebo controlled studies and Active comparators first in the case of active comparator trials, followed by a total column (if applicable).

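### Total time on study is set as mean time × Safety N, which silently imputes the mean for any dosed subject without a final-visit date

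*SAP*

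**What the plan says.** SAP section 8.1 defines individual time as "Time on Study (Days) = Date of Visit 4 (end of study visit)/withdrawal visit - Date of Baseline visit + 1". Months and years follow by "dividing the time on study calculated in days by 28 and 365 respectively". The total, in months and in years, is then obtained by "taking the mean time on study in months/years respectively and multiplying by the number of subjects in the Safety Population".

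The multiplier is broad. In SAP section 6.2, "The Safety Population is defined as all subjects who received at least part of one dose" of Optivate.

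The mean is not necessarily taken over that same number. SAP section 7.1 states: "Continuous variables will be summarised using the number of observations (n), mean, 95% confidence interval for the mean". SAP section 14.2.4 separates the population N in column headings from the n used for "the descriptive statistics representing the number of subjects in the population with the respective data".

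On gaps in the data, SAP section 7.3 says "There will be no imputation for missing data". Protocol section 9 lists "Lost to follow-up" among the reasons for stopping, and only asks withdrawing subjects to complete the final assessments. SAP section 7.4 expects withdrawn subjects to complete the End of Study pages. Neither document names an end date for a dosed subject who has no final visit.

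**The concern.** Mean × N reproduces a total only when the mean was taken over the same N. A subject who receives Optivate at Visit 1 and later cannot be reached counts in N, but has no date from which to compute a time. Read as written, the rule gives that subject the average time of the subjects who have dates.

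The total matters because the programme has expressed safety in patient-time before. The protocol's Introduction cites 130 patient-years from two earlier studies with no inhibitor cases, and a total from this study could be quoted in the same way. With 12 planned subjects, each is about 8% of the headcount (1/12 = 8.3%), so one undated subject is visible in the result.

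The rule is also inconsistent with the rest of the SAP. The per-month and per-year summaries in sections 9.2.4 and 9.2.5 divide by each subject's own time on study. An undated subject has no denominator there and drops out, yet is counted at average time in the section 8.1 total.

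**Working it through.** The documents state no total time on study, so there is no figure to reproduce. The check is whether the rule equals the sum of individual times, and by how much it departs when it does not.

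**Inputs from the documents**
- Dosed subjects: 12 planned (SAP section 4.3), so N = 12.
- Completer time: 39 to 52 weeks after baseline (Protocol section 7.4), i.e. 273 to 364 days.
- Year = 365 days, month = 28 days (SAP section 8.1).

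**Assumptions** (the documents give no loss rate or timing)
- Zero, one or two subjects without an end date.
- Loss at day 1, week 4, 16 or 26, plus a late loss at week 50.
- All completers have the same time.

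**Formula**

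Let n be the number of subjects with a date.

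- SAP total = (sum of dated times / n) × N
- Error = (N − n) × (mean time of dated subjects − mean true time of undated subjects)

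**Step 1: all dates present.** With n = N the error is zero. Invented example with two early withdrawals that have dates: 273, 280, 300, 310, 320, 333, 340, 350, 360, 364, 60 and 120 days. The sum is 3410, and (3410/12) × 12 = 3410 days, which is 9.34 years or 121.8 months of 28 days. Early withdrawals with a visit enter at their own shorter times.

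**Step 2: undated subjects who left early.** For completers at 39 weeks the SAP total is 12 × 273 = 3276 days (8.98 years). For completers at 52 weeks it is 12 × 364 = 4368 days (11.97 years). Cells show true years and the excess of the SAP total over them.

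| Lost at | One, 39 wk | Two, 39 wk | One, 52 wk | Two, 52 wk |
|---|---|---|---|---|
| Day 1 | 8.23 (+9.1%) | 7.49 (+19.9%) | 10.97 (+9.1%) | 9.98 (+19.9%) |
| Week 4 | 8.30 (+8.1%) | 7.63 (+17.6%) | 11.05 (+8.3%) | 10.13 (+18.2%) |
| Week 16 | 8.53 (+5.2%) | 8.09 (+10.9%) | 11.28 (+6.1%) | 10.59 (+13.0%) |
| Week 26 | 8.73 (+2.9%) | 8.48 (+5.9%) | 11.47 (+4.3%) | 10.97 (+9.1%) |

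Example: one lost at week 26, completers at 39 weeks. True total = 11 × 273 + 182 = 3185 days; 3276/3185 = 1.029.

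**Step 3: undated subjects who left late.** Completers at 39 weeks, loss at week 50 (350 days):
- One: 11 × 273 + 350 = 3353 days; 3276/3353 − 1 = −2.3%.
- Two: 10 × 273 + 700 = 3430 days; 3276/3430 − 1 = −4.5%.

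**Step 4: summing the dated times alone is not enough.** In the week-26 example this gives 11 × 273 = 3003 days against 3185, or −5.7%. An end-date rule is needed as well as a sum.

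**The case against.** The strongest reply is that the case is narrow. Time on study already ends at a withdrawal visit, SAP section 7.4 expects the final pages from every withdrawn subject, and Protocol section 4.2 gives remaining subjects an End-of-Study visit when the trial stops. Protocol section 5.3 also excludes people with a history of unreliability. Only a dosed subject who disappears without a recorded final visit is affected. The CRF and the table mock-ups are not available here, so it cannot be checked whether an end date is captured for such a subject. All of this stands. It makes the problem conditional, but does not supply the missing rule: an instruction to complete pages cannot produce a visit for someone who cannot be reached.

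It also stands that little depends on the total. It belongs to the study-duration summary (Table 14.1.2). Adverse event percentages use subjects as denominator, the primary endpoint uses inhibitor status by visit and exposure days to a positive result, and consumption rates use each subject's own time.

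A reader might infer that the rule always inflates patient-time in the product's favour, or that every early withdrawal is credited with average exposure. The documents support neither. Dated withdrawals enter at their own time, and the sign depends on whether the undated subject stayed for less or more than the mean. A late loss is possible: Visit 4 is postponed until 100 exposure days are reached, a twice-weekly regimen may be agreed case by case (Protocol section 6.2.2.1), and the last two subjects may be treated for a shorter period.

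**Conclusion.** The point holds as a conditional defect of minor severity. When a Safety subject lacks a Visit 4 or withdrawal-visit date, mean × N imputes the mean for that subject, contrary to SAP section 7.3. With all dates present the error is zero.

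Under the assumed losses by week 26, the excess is about 3% to 9% for one undated subject of 12 and 6% to 20% for two. With loss at week 50 and completers at week 39, the total is instead about 2% to 5% too low. These ranges rest on assumed numbers and timing of losses, and show how sensitive the total is rather than what to expect. No planned inference or rate is affected; the risk is confined to the total being quoted as patient-time.

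**What to change.** In SAP section 8.1:

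1. Define total time on study as the sum of individual times on study in the Safety Population.
2. For a subject without a Visit 4 or withdrawal visit, end at the last documented contact (visit, diary entry or telephone contact), and state this as a derivation rule so that it does not conflict with section 7.3.
3. Show n beside N in Table 14.1.2.

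Do not use the last infusion date as the end date in the per-month and per-year formulas of sections 9.2.4 and 9.2.5. It closes follow-up on an exposure day: a subject lost straight after the Visit 1 dose would have 1 exposure day in 1 day, i.e. 1/1 × 365 = 365 per year. A last contact on the same day would do the same, so the SAP should also say whether such a subject enters those rate summaries or is only listed.

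The cost is a few SAP sentences. The contact dates should largely exist already, since the diary dates each home dose. Reported total exposure may be slightly lower, and nothing changes if every subject has a final-visit date.

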8.2. DEMOGRAPHIC AND OTHER BASELINE CHARACTERISTICS

Age at screening, gender, race and ethnicity will be summarised for the Safety Population.

Time since diagnosis (years) will be calculated as:

((Date of Informed Consent) - (Date of Diagnosis))/365

Should the day of diagnosis be missing then it will be taken as 01. Should the month of diagnosis be missing it will be taken as January.

Time since diagnosis, lowest basal FVIII level, gene defect (intron 1 inversion, intron 22 inversion, other) and family history of Haemophilia A will be summarised for the Safety Population.

Sponsor: BPL
Protocol: 8VWF07

Version: 1.0

Statistical Analysis Plan

Mutations from previous genotyping and details of family members with a history of Haemophilia A will be listed only.

8.3. MEDICAL HISTORY

Medical history will be coded using MedDRA Version 16.1.

Medical history will be listed. The listing will indicate whether or not an event is ongoing, as noted in the CRF.

Medical history will be summarised using the Safety Population. Summaries will be provided for past events, ongoing events and all events (past and ongoing). In the summary tables, system organ classes will be ordered alphabetically. Preferred terms within system organ class will also be order alphabetically.

8.4. PRIOR AND CONCOMITANT MEDICATIONS

Prior and concomitant medications will be coded to the preferred name using WHO Drug version 1 March 2013. Note, prior medications do not include FVIII containing products and/or blood products taken prior to entering the study. These are listed separately.

Prior medications are defined as those medications started prior to the date of the first infusion of Optivate[®]. Concomitant medications are those taken on or after the date of the first infusion of Optivate[®]. Note, a medication started prior to but continuing after the first infusion of Optivate[®] will be classed as both prior and concomitant.

Should the start day of the medication be missing, for the purposes of assigning prior/concomitant status, the day will be taken to be 01, unless the month and year are the same as the month and year of first infusion of Optivate®, in which case the date of first infusion of Optivate® will be taken.

Should the start day and month be missing, for the purposes of assigning prior/concomitant status, the day and month will be taken to be 01 January, unless the year is the same as the year of first infusion of Optivate[®], in which case the date of first infusion of Optivate[®] will be taken.

All medications will be listed in order of start date. The listing will identify prior medications.

Prior and concomitant medications will be summarised separately for the Safety Population. Summaries will show the number and percent of subjects taking medications coded to the given preferred term. Summary tables will be sorted alphabetically by preferred name.

Sponsor: BPL

Protocol: 8VWF07

Version: 1.0

Statistical Analysis Plan

9. EFFICACY

9.1. PRIMARY EFFICACY ENDPOINT AND ANALYSIS

The primary efficacy endpoint is the assessment of immunogenicity of Optivate® by monitoring plasma inhibitor levels for at least 100 EDs for each subject.

Pre-bolus blood samples for quantitative assays will be collected at the Screening Visit, Baseline Visit (Visit 1), Visit 2, Visit 3, the End of Study Visit (Visit 4) and possibly also at unscheduled visits if deemed necessary.

Inhibitor screen data will be listed only.

Quantitative inhibitor results will be listed.

Summaries of quantitative inhibitor levels will be based on both the Per Protocol and Safety populations.

At each visit, the number and percentage of subjects with positive (\geq 0.6 Bethesda Units) and negative (< 0.6 Bethesda Units) results will be summarised.

Shift tables cross tabulating positive/negative status (based on the Bethesda assay) at the Baseline Visit against those at Visits 2, 3 and 4 will be presented. Shifts from the Baseline Visit to any unscheduled visits will also be summarized. Note, should a subject have more than one unscheduled visit then the worst case assessment (positive) will be used in the summary.

The number of exposure days until development of inhibitors (positive status) will be summarized.

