10.8 Determination of Sample Size

No formal sample size calculation was performed, as no formal hypothesis testing is planned. The sample size of 10 evaluable subjects was agreed with the German regulatory authority as part of the licencing agreement for Optivate[®]. Therefore for this study 12 subjects will be enrolled to ensure data for 10 evaluable subjects.

11.

INVESTIGATOR'S STATEMENT

Multicentre, Non-controlled, Prospective, Post-Marketing Safety Study Following Long-Term Prophylactic Optivate[®] Treatment in Subjects with Severe Haemophilia A.

STUDY CODE: 8VWF07

FINAL PROTOCOL

Version 4, 30 November 2015

I have been adequately informed about the development of the IMP to date and agree that this study protocol contains all the information required to conduct the study.

I will provide copies of the study protocol and all product information relating to prior product experience furnished to me by the Sponsor/CRO to all staff responsible to me who participate in this study. I will discuss this material with them to ensure that they are fully informed regarding the product and the conduct of the study.

The information contained in this document is CONFIDENTIAL and, except to the extent necessary to obtain informed consent, may not be disclosed, unless such disclosure is required by government regulation or local customs or law. Persons to whom the information is disclosed must be informed that the information is CONFIDENTIAL and cannot be disclosed by them.

By my signature below I agree to conduct this clinical trial in accordance with the protocol, Good Clinical Practice (GCP), government regulations, and local customs or laws, including those applying to institutional/ethics review and informed consent.

I agree to ensure the confidentiality of the subjects enrolled under my care; however, I agree to make their medical records available to authorised representatives of the CRO; authorised representatives of Bio Products Laboratory Ltd., the sponsor of this clinical trial; and relevant regulatory authorities.

I have read the Summary of Product Characteristics for Optivate[®] and protocol, and I am aware of my responsibilities as a Principal Investigator.

Signature:		Date:
	Principal Investigator	
Name:		
	(Printed)	

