4.3. DETERMINATION OF SAMPLE SIZE

No formal sample size calculation was performed, as no formal hypothesis testing is planned. The sample size of 10 evaluable subjects was agreed with the German regulatory authority as part of the licensing agreement for Optivate[®]. Therefore for this study 12 subjects will be enrolled to ensure data for 10 evaluable subjects.

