14.2.5.2. Table Conventions

- Units will be included where available
- If the categories of a parameter are ordered, then all categories between the maximum and minimum category should be presented in the table, even if n=0 for all treatment groups in a given category that is between the minimum and maximum level for that parameter. For example, the frequency distribution for symptom severity would appear as:

Severity	N
Rating	
severe	0
moderate	8
mild	3

Where percentages are presented in these tables, zero percentages will not be presented and so any counts of 0 will be presented as 0 and not as 0 (0%).

- Unless otherwise specified in the mock table, where the categories are not ordered (e.g., Medical History, Reasons for Discontinuation from the Study, etc.), then only those categories for which there is at least 1 subject represented in 1 or more groups should be included.
- Unless otherwise specified, the estimated mean and median for a set of values should be printed out to 1 more significant digit than the original values, and standard deviations should be printed out to 2 more significant digits than the

Sponsor: BPL
Protocol: 8VWF07

Version: 1.0

Statistical Analysis Plan

original values. The minimum and maximum should report the same significant digits as the original values. For example, for systolic blood pressure:

N	XX
Mean	XXX.X
Std Dev	X.XX
Median	XXX.X
Minimum	XXX
Maximum	XXX

- P-values should be output in the format: "0.xxx", where xxx is the value rounded to 3 decimal places. Any p-value less than 0.001 will be presented as <0.001. If the p-value should be less than 0.0001 then present as <0.0001. If the p-value is returned as >0.999 then present as >0.999
- Percentage values should be printed to one decimal place, in parentheses with no spaces, one space after the count (e.g., 7 (12.8%), 13 (5.4%)). Unless otherwise noted, for all percentages, the number of subjects in the analysis population for the treatment group who have an observation will be the denominator. Percentages after zero counts should not be displayed and percentages equating to 100% should be presented as 100%, without any decimal places.

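### The primary inhibitor endpoint is summarised with no confidence interval and no stated proportion of treated subjects who ever become positive

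*SAP*

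**What the plan says.** SAP 9.1 defines the endpoint: "The primary efficacy endpoint is the assessment of immunogenicity of Optivate® by monitoring plasma inhibitor levels for at least 100 EDs for each subject". The planned outputs are:

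- listings of the screen and quantitative results;
- a summary by visit ("At each visit, the number and percentage of subjects with positive" and negative results, cut at 0.6 BU);
- shift tables from Baseline to Visits 2, 3 and 4, and separately to unscheduled visits;
- a summary of EDs until an inhibitor develops.

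The quantitative summaries are made for both the Per Protocol and Safety populations. SAP 6.1 makes Per Protocol (at least 100 EDs completed) the primary one.

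The general rules add no interval. SAP 7.1 gives a 95% interval for the mean of a continuous variable, but says "Categorical variables will be summarised using number of observations (n), frequency and percentages of subjects". Protocol 10.3 treats categorical data the same way, and Protocol 10.6.1 names no interval for the inhibitor result. By contrast, SAP 9.2.1 and 9.2.2 give 95% intervals and p-values for the secondary recovery comparisons.

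On sample size, Protocol 10.8 says "No formal sample size calculation was performed, as no formal hypothesis testing is planned". SAP 4.3 adds "The sample size of 10 evaluable subjects was agreed with the German regulatory authority" and "Therefore for this study 12 subjects will be enrolled to ensure data for 10 evaluable subjects".

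**The concern.** Inhibitor formation is the reason for the study, yet it is the outcome with no planned measure of precision. Zero cases is a likely result: Protocol section 2 reports none in about 130 patient-years in previously treated patients. In that event the ED-to-inhibitor summary is empty and the shift tables show no shifts. What remains is a zero count by visit.

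Two features of the denominator add to this.

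- Protocol section 9 lists inhibitor development among the reasons a subject may stop treatment. Such a subject, if stopped before 100 EDs, is not in the Per Protocol set.
- SAP 7.1 keeps unscheduled-visit data out of the summary tables, and SAP 9.1 readmits them only in the unscheduled-visit shift summary. Protocol 8.1.1 provides for inhibitor samples at unscheduled visits for excessive or emergency bleeding, where a case could well be found.

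At stake is whether the report lets a reader see how little a zero from 10 to 12 subjects excludes.

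**Working it through.** **Inputs.** Minimum evaluable n = 10 and planned enrolment 12 (SAP 4.3; Protocol 10.8). The event is at least one inhibitor in a subject. The documents give no confidence level for a proportion. I assume 95% two-sided, the level the SAP uses elsewhere.

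**The plan's own figure.** There is none to reproduce. The 10 was agreed with the regulator, with no target rate, power or precision stated.

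**Exact (Clopper-Pearson) limits, no events.** Upper limit U = 1 − 0.025^(1/n).

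- n = 10: 0.025^(1/10) = 0.6915, so U = 0.3085, or 30.8%. Check: (1 − 0.3085)^10 = 0.0250.
- n = 12: 0.025^(1/12) = 0.7354, so U = 0.2646, or 26.5%.

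**One event.** The lower limit is 1 − 0.975^(1/n). The upper limit is the 0.975 quantile of Beta(2, n − 1).

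- 1/10: 0.3% to 44.5%.
- 1/12: 0.2% to 38.5%.

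**Sensitivity to method, upper limit for no events:**

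| Method | 0/10 | 0/12 |
|---|---|---|
| Exact, two-sided 95% | 30.8% | 26.5% |
| Rule of three (3/n) | 30.0% | 25.0% |
| Wilson | 27.8% | 24.2% |
| Exact, one-sided 95% | 25.9% | 22.1% |
| Jeffreys | 21.7% | 18.5% |

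**Chance of seeing no inhibitor in 10 subjects, (1 − p)^10.** True rate 5%: 0.95^10 = 60%. True rate 10%: 0.90^10 = 35%. True rate 20%: 0.80^10 = 11%.

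**Effect of the denominator (illustration).** Suppose 12 subjects are treated, one stops before 100 EDs with an inhibitor, one withdraws for another reason, and 10 reach 100 EDs without a positive test. The Per Protocol result is 0/10 (0% to 30.8%). The Safety result is 1/12 = 8.3% (0.2% to 38.5%). The primary table shows no case although one occurred.

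**The case against.** The strongest reply is that this is a descriptive study with an agreed size. The documents say so openly, note that the sample is smaller than the guideline's, and neither plan a claim of a low rate nor set a threshold. Every result is listed, and anyone can compute an interval from 0/n. All of that stands. A reader might infer that the plan conceals its imprecision or that 10 subjects is itself an error; the documents support neither. But a descriptive interval needs no hypothesis, and the SAP already gives one for means. Fixing it in advance also settles numerator, denominator and method before the data are seen.

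A reader might also infer that a null result would appear as a lone zero. It would not: negatives are tabulated beside positives, SAP 14.2.4 puts N in the column heading, and n is shown. Whether 0% is printed is unsettled. SAP 7.1 says how to format 0%, while SAP 14.2.5.2 says "Percentages after zero counts should not be displayed".

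Nor is a whole-study case count wholly absent. The n in the ED-to-inhibitor tables gives it in both populations. Inhibitor development is automatically serious, so reported cases would also enter the serious TEAE table as a number and percentage of the Safety Population. SAP 7.4 carries withdrawn subjects' final assessments into the Safety summaries under End of Study. These recover a count when cases occur. They do not give a defined ever-positive proportion with its precision, and a zero shows in the serious TEAE table only by absence.

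Finally, the table mock-ups are a separate attachment that I have not seen. An interval there cannot be excluded, but the SAP text does not call for one.

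**Conclusion.** The gap is real but modest, and the remedy is a cheap improvement. As written, SAP 9.1 attaches no interval to the primary result, defines no ever-positive proportion, and makes primary a set that can lose a case through early stopping.

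For no events, the unstated exact upper limit is 30.8% with 10 subjects and 26.5% with 12. These figures assume a two-sided 95% Clopper-Pearson interval, zero events and exactly those denominators. Zero is a hypothetical outcome, 10 is a minimum, and replacement of withdrawals could take the Safety Population above 12. Across the methods tried, the limit runs from 21.7% to 30.8% for 0/10 and from 18.5% to 26.5% for 0/12, so the message does not depend on the method.

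The 30.8% should not be read as a bound on the inhibitor rate when it comes from 100-ED completers. That set is partly selected by the outcome, so an interval on it does not cover subjects who stopped because of an inhibitor.

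**What to change.** 1. In SAP 9.1, add as the headline the number and percentage of Safety Population subjects with an inhibitor at any time after the first Optivate dose, at scheduled or unscheduled visits, with a Clopper-Pearson 95% interval. Define a case by the protocol's own criteria: at least 0.6 BU confirmed on a repeat test of a separate sample (Protocol 7.9.2), supported by a recovery result (Protocol 8.1.1).
2. Show the same statistic for the 100-ED completers as supportive only, with a note that subjects withdrawn for an inhibitor before 100 EDs are excluded.
3. In Protocol 10.8 and SAP 4.3, state the expected precision for the Safety Population, for example upper limits of 26.5% for 0/12 and 30.8% for 0/10.
4. Reconcile SAP 7.1 with SAP 14.2.5.2 on printing 0%.

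The cost is one extra statistic, a footnote, a sentence on precision and a less favourable-looking headline. No subjects, visits or samples are added. One limit remains: some Safety subjects may have fewer than 100 EDs, including the last two enrolled if the study stops first. The proportion should be read beside the ED summary already planned for that population.
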